### **10.3 Clinical follow-up**

Women undergoing medication abortion generally undergo clinical follow-up to ensure that the abortion is complete. Follow up to ensure no ongoing pregnancy at approximately 7-14 days after the initial visit may be completed in one of three ways: 1) an in-person clinic visit with ultrasound, 2) an in-person clinic visit with serum hCG (in the case that serum hCG was measured on the day the Mifeprex® was prescribed; the follow-up laboratory test may be performed at an off-site laboratory), or 3) a telephone follow-up with the clinic at approximately 1 week after Mifeprex® was taken, followed by a urine pregnancy test at 3-4 weeks (at home) post medication abortion. Results from these measures will be documented in the clinical record and later abstracted for data collection. No study-related activities will be performed as part of this clinical follow-up. Participants with ongoing pregnancy will be managed according to the standard practice at the site, and may include an additional dose of misoprostol, repeating Mifeprex® and misoprostol, or vacuum aspiration. Those who need additional medications will receive either a prescription or referral to another facility. If the participant is referred to another facility for a vacuum aspiration or other treatment related to the medication abortion or if the participant spontaneously goes to another facility, the site PI or delegate will contact the referral site to document the treatment given, abortion outcome (if relevant), and any AEs or SAEs. No study activities will take place at follow-up clinical visits, although clinical information recorded at these visits will be later abstracted from the patient's record (see section 9.1).

### **10.4 Day 14 Survey**

On Day 14 after the prescription is sent, patient participants will be sent by email or text message, depending on their preference, a link to an online survey about their overall satisfaction with the medication abortion process and to obtain information about whether the abortion has been completed (see Day 14 Survey), and whether she has sought care at another facility. If she did obtain care at another facility, we will ask for details of the care given to determine if an AE or SAE has occurred, and we will follow up with the participant by telephone to obtain additional details as needed. If the participant reports being seen at another facility, we will alert the site PI. If a participant prefers, or if she does not respond to the email link, she may be contacted by telephone to complete the survey over the phone or sent reminders by text message. If the follow-up for the abortion is not yet complete at the Day 14 survey, we will instruct the patient to contact the clinic and ask for permission to contact them again later. If they do not respond to the Day 14 survey, participants will be contacted up to three times.

### **10.5 Data Abstraction**

As noted above in section 9, de-identified data about the clinical visits of participants consenting for the study will be abstracted from the electronic medical record system of the participating sites. This includes clinical information including demographics (age, parity, race, ethnicity), initial visit information (date of service, gestational age, past medical history, medications, laboratory values), and follow-up visit information (date(s) of service, treatment given, symptoms, outcome of abortion, adverse events, and other follow-up care). The site PI will perform a chart review for each participant 6 weeks

after enrollment. De-identified data will be entered into a REDCap electronic form. As noted above, the site PI will supervise the data abstraction and replace the participant name with the Study ID prior to transferring the data to the UCSF research team.

The study team will request consent from participants to obtain access to medical record data related to the abortion, pregnancy, and subsequent birth (if relevant) including through records' release from other facilities. This will enable the study team to collect data on visits to other medical facilities and on pregnancy outcomes for participants.

## 11 PROVIDER ACTIVITIES

### 11.1 Needs assessment, training, and post-training evaluation

At baseline, we will conduct a needs assessment focused on provider knowledge of medication abortion, comfort with dispensing Mifeprex®, and anticipated challenges of dispensing Mifeprex®. This needs assessment will be informal, and conducted through conversations with the site investigator(s). Each of the providers interested in being involved in medication abortion provision at the study sites will be required to participate in a training. The training will focus on gaps in knowledge identified in the baseline needs assessment, including specifics about the medication abortion protocol, mifepristone and misoprostol mechanisms of action, side effects, potential complications and follow up. After the training, providers will be asked to complete a brief informal evaluation, which will serve to improve future trainings on the topic.

#### 11.1 Provider interviews

At the end of the study period, providers will be invited to participate in a 30-minute in-depth interview by telephone or in person. The interview will explore the providers' experiences with providing medication abortion and any challenges faced. Providers who participate in prescribing medication abortion to study patients may decline to participate in the interview. Providers will be asked for oral consent to the interview and consent to record the interview will be confirmed and documented.

## 12 ADVERSE EXPERIENCE REPORTING AND DOCUMENTATION

### 12.1 Adverse Events

Adverse Events (AEs) are to be reported only for untoward medical events that occur in participants after they have enrolled in the study. Only new untoward events, or a worsening of an existing condition, are considered AEs. Conditions that were present before enrollment into the study, and that remain stable or improve during the study, are not considered AEs. Only serious or unexpected AEs that are possibly, probably, or definitely related to the research will be submitted to the UCSF IRB. Diversion of Mifeprex® obtained in the study to someone other than the participant will also be considered an AE.

Information regarding AEs or SAEs may be first obtained by the clinical or study staff, as both will communicate with the participant at her visits and by phone.

Details about each AE or SAE will be recorded on an AE/SAE Form. This form will require the following information to be collected: diagnosis, onset date, resolution date, source of information, severity, treatment given, relationship to the study, action taken, and comments.

The physician site PI will have safety oversight of participants at the site, will assess AEs and SAEs, and will report them to the study PI and research team, who will then report to the UCSF IRB as

needed. The site PI, in consultation with the study PI, will determine the relationship of the AE to study treatment as definitely related, probably related, possibly related, or unrelated; and the severity of the AE as mild, moderate or severe. For AEs or SAEs that have not resolved at the time of learning of the event, the study team and the site PI will monitor the event until the event is resolved or has stabilized.

The study PI is also responsible for reporting all AEs to all relevant Institutional Review Boards (IRBs). All AEs that are related to the study and are serious or affect IRB approval will be reported by the PI to the relevant IRBs according to IRB requirements. UCSF requires that an internal (on-site) AE that the PI determines to be related to the study and serious or unexpected shall be reported within 5 working days of the UCSF PI's knowledge. External (off-site) AE's that change the study risks/benefits or requires a UCSF IRB modification must be reported within 10 working days of the UCSF PI's knowledge. Diversion of Mifeprex® will be reported to the FDA within 15 days of the UCSF PI's knowledge.

An AE is any untoward medical occurrence in a clinical investigation of a patient administered a pharmaceutical product and that does not necessarily have a causal relationship with the treatment. An AE is therefore any unfavorable and unintended sign (including an abnormal laboratory finding), symptom or disease temporally associated with the administration of an investigational product, whether or not related to that investigational product. An unexpected AE is one of a type not identified in nature, severity, or frequency in the current Mifeprex® label or of greater severity or frequency than expected based on the information in the label.

The following definitions apply to adverse events occurring in clinical studies involving drugs:

- An AE is any health-related reaction, effect, toxicity or abnormal laboratory result that a participant experiences during the course of the study, irrespective of relationship to study product use.

In this study, the following routine study measurements will not be considered AEs because they are anticipated participant outcomes:

- Abortion
- Symptoms associated with medication abortion (pain, vaginal bleeding, fever, chills, nausea, vomiting, headache, weakness, dizziness and diarrhea), unless they are so severe as to meet the criteria for a SAE (see section 12.2 below)

### 12.1.1 Adverse Event Severity

The National Cancer Institute's Common Terminology Criteria for Adverse Events (CTCAE) Version 3.0 should be used to assess and grade AE severity, including laboratory abnormalities judged to be clinically significant. Table 1 below should be used to grade severity. It should be pointed out that the term "severe" is a measure of intensity and that a severe AE is not necessarily serious.

**Table 1. AE Severity Grading**

Severity (Toxicity Grade)	Description
Mild (1)	Transient or mild discomfort; no limitation in activity; no medical intervention or therapy required. The subject may be aware of the sign or symptom but tolerates it reasonably well.
Moderate (2)	Mild to moderate limitation in activity, no or minimal medical intervention/therapy required.

Severe (3)	Marked limitation in activity, medical intervention/therapy required, hospitalizations possible.
Life-threatening (4)	The subject is at risk of death due to the adverse experience as it occurred. This does not refer to an experience that hypothetically might have caused death if it were more severe.

### 12.1.2 AE Relationship to Study Drug

The relationship of an AE to the study drug should be assessed using the following the guidelines in Table 2.

**Table 2. AE Relationship to Study Drug**

Relationship to Drug	Comment
Definitely	Previously known toxicity of agent; or an event that follows a reasonable temporal sequence from administration of the drug; that follows a known or expected response pattern to the suspected drug; and that is not explained by any other reasonable hypothesis.
Probably	An event that follows a reasonable temporal sequence from administration of the drug; that follows a known or expected response pattern to the suspected drug; and that is unlikely to be explained by the known characteristics of the subject's clinical state or by other interventions.
Possibly	An event that follows a reasonable temporal sequence from administration of the drug; that follows a known or expected response pattern to that suspected drug; but that could readily have been produced by a number of other factors.
Unrelated	An event that can be determined with certainty to have no relationship to the study drug.

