### **12.2.1 Serious Adverse Event Reporting**

Study sites will document all SAEs that occur (whether or not related to study drug) per [UCSF IRB Guidelines](#). The collection period for all SAEs will begin after informed consent is obtained and end six weeks after the visit where Mifeprex® is prescribed.

In accordance with the standard operating procedures and policies of the local IRB/the site PI will report SAEs to the IRB.

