## 14.1 Study Stopping Criteria

The following criteria will be used to determine whether and when to stop the study prior to meeting recruitment targets:

- If there are 3 cases where mail-order delivery of the medication is delayed by more than 7 days, we will temporarily halt the study and assess the need to adjust the inclusion criteria to less than 57 days' gestation (instead of 63 days) in order to eliminate the possibility that participants receive mifepristone past 70 days' gestation. We will also investigate all cases of medication delivery being delivered more than 4 days after the prescription was sent to understand the factors that contributed to delay and address them. In addition, we will contact all participants on Day 3 after the prescription was sent, and if they have not received the medications, we will encourage them to contact the study site to make other arrangements to obtain the mifepristone and misoprostol.
- If there are 12 cases (3% of total sample) where the participant takes mifepristone after 70 days' gestation, we will assess the need to stop the study. All cases of use past 70 days will be investigated to understand why they occurred and efforts will be made to ensure such errors do not occur in the future. There is evidence that the medication abortion regimen works through 11 weeks of gestation (Kapp, Eckersberger et al. 2019); with regard to clinical safety, this is why the research team feels comfortable with 12 potential cases beyond 70 days gestation. Finally, if 1% of participants (4 cases) take the mifepristone after 84 days (12 weeks), we will stop the study.
- Every AE and SAE will be reviewed by the study PI, and if there is a pattern of definitely-, probably-, or possibly-related SAE/AEs that raise concerns about the safety of the mail-order model of dispensing mifepristone, the study will be stopped. Based on evidence that 0.3% of medication abortions have serious adverse events (Upadhyay, Johns et al. 2018), we will stop the main study if the number of SAEs fall outside of a 95% confidence interval as estimated in a sample of 465 (-0.24% to 0.84%) (minimum sample of 440 plus 25 pilot study participants). Thus we will stop the study if more than 0.84% (n=4) of abortions result in an SAE that is possibly or probably related to the study intervention.

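### Table 2 lets a known toxicity be graded Definitely without the time sequence that Probably and Possibly require, and the numeric SAE stop in Section 14.1 is the count exposed to this

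*Combined protocol and SAP*

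**What the plan says.** Section 12.1.2 introduces the causality scale with "The relationship of an AE to the study drug should be assessed using the following the guidelines in Table 2". Table 2 then gives four grades.

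- **Definitely** has two limbs. It begins "Previously known toxicity of agent; or an event that follows a reasonable temporal sequence from administration of the drug", goes on to a known or expected response pattern, and ends "and that is not explained by any other reasonable hypothesis".
- **Probably** requires a reasonable time sequence, a known or expected pattern, and that the patient's clinical state or other interventions are unlikely to explain the event.
- **Possibly** requires the same time sequence and pattern, "but that could readily have been produced by a number of other factors".
- **Unrelated** is "An event that can be determined with certainty to have no relationship to the study drug".

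The grade is used in three places. Section 12.1 filters IRB reports: "Only serious or unexpected AEs that are possibly, probably, or definitely related to the research will be submitted to the UCSF IRB". In Section 14.1, the third stopping criterion first refers to a pattern of definitely, probably or possibly related events. It then sets a numeric stop at more than 0.84% (n=4), counting cases where "abortions result in an SAE that is possibly or probably related to the study intervention".

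On timing, Section 12.2.1 states: "The collection period for all SAEs will begin after informed consent is obtained". Section 10.1 tells patients to expect delivery within 3 business days.

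**The concern.** A causality scale should ask for more evidence at each step up. Here the first limb of the top grade asks for less than the lowest related grade. Two events of a type known for this drug show the problem:

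- An SAE after dosing that something else could readily explain fits Possibly, and also fits the first limb of Definitely.
- An SAE between consent and the first dose should be Unrelated to the drug, yet also fits the first limb of Definitely.

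This is not a rare corner of the scale. Section 1 names serious infection, bleeding that needs intervention, and transfusion as known complications. Under Section 12.1 the common label symptoms become adverse events only when they are severe enough to be SAEs. Many of the SAEs to be expected will therefore be of a known type, and 15 to 20 sites could grade the same event differently. What is at stake is the ordering of the scale and, through it, a stopping count that turns on about four events.

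**Working it through.** **1. The grades side by side (Table 2)**

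| Grade | Time sequence | Known pattern | Other causes |
|---|---|---|---|
| Definitely, first limb | not required | known toxicity | not addressed on the natural reading |
| Definitely, second limb | required | required | no other reasonable explanation |
| Probably | required | required | unlikely to explain it |
| Possibly | required | required | could readily explain it |
| Unrelated | – | – | no relationship, with certainty |

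The exclusion clause in the Definitely row is the third of three parallel clauses describing *an event*, so grammar ties it to the second limb. The semicolons leave open that it governs both limbs. Even then, the first limb has no time requirement.

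**2. Can an event before dosing reach Table 2?** Yes. Adverse events count from enrollment (Section 12.1) and SAEs from consent (Section 12.2.1). One definition in Section 12.1 requires temporal association with administration. Another in the same section counts anything during the study irrespective of product use.

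**3. Which counts depend on the grade?**

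- IRB filter (Section 12.1): pools the three related grades, so a move from Possibly to Definitely changes nothing. Section 18.2 also sends serious events to the IRB regardless of causality.
- Pattern-based stop (Section 14.1): pools the three related grades, so no change.
- Clinically significant adverse events (Section 4.3): defined by event type, so no change.
- Numeric SAE stop (Section 14.1): names only possible and probable events. An SAE graded Definitely is not counted.

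A pooled count changes only for an event that would otherwise be Unrelated. That grade needs certainty, so in practice this mainly means an event before dosing.

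**4. Size for the numeric stop.** The plan gives no figure for causality grading. For the stop itself, 0.0084 × 465 = 3.9 and 4/465 = 0.86%, so the fourth counted SAE crosses the limit. (At 0.3% and n = 465 the Wald interval is −0.20% to 0.80%. The printed −0.24% to 0.84% corresponds to n = 400. Since 0.00797 × 465 = 3.7, the trigger is four either way, and this is a separate matter.)

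Let p be the true rate of related SAEs and f the share graded Definitely by either limb, and so not counted. Then X ~ Binomial(465, p(1 − f)) and P(stop) = P(X ≥ 4).

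Example with p = 1% and f = 50%: the counted rate is 0.5% and the mean is 465 × 0.005 = 2.3. P(0), P(1), P(2) and P(3) are about 0.097, 0.227, 0.265 and 0.205. They sum to about 0.794, so P(X ≥ 4) is about 0.21.

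| f | 0% | 25% | 50% | 75% | 100% |
|---|---|---|---|---|---|
| p = 0.3% (plan's rate) | 5.3% | 2.2% | 0.6% | 0.05% | 0% |
| p = 1% (assumed) | 68% | 46% | 21% | 3% | 0% |

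If the rule is read as needing a fifth event, the p = 1% row becomes 50%, 27%, 9%, 0.7% and 0%.

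The shares f and the 1% rate are assumptions. An SAE properly graded Definitely under the second limb also drops out, so the first limb's own effect is only the amount by which it raises f.

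**The case against.** The strongest reply is that this is loose drafting in a guidance table. Table 2 is described as guidelines, and under Sections 12.1 and 15 the site PI, in consultation with the study PI, determines the relationship. To call something a toxicity of the agent is arguably already to attribute it to the agent, and no sensible investigator would so describe a bleed before any tablet was taken. The numeric stop refers to the study intervention, whereas Table 2 grades relation to the drug. The stop also counts abortions that result in an SAE, which an event before dosing hardly fits.

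Much of this stands. A reader might infer that known-type SAEs are graded automatically. The documents do not support that, because a judgement is made each time. A reader might also infer that related-event counts are wrong. That is not shown, because the pooled uses do not change when an event moves between related grades. Nor do the documents support a claim that unrelated events would fill the stopping count and halt the study falsely. They give no rate for certainly unrelated known-type SAEs, and an SAE after dosing with a plausible other cause is normally Possibly already.

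Two things are not answered. A criterion that presupposes attribution gives no test for it, and Table 2 holds the only grading criteria that the sites have. The documents also offer no separate scale for relation to the intervention, so the Table 2 grade is likely to be the one used in Section 14.1.

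A further objection is that replacing *or* with *and* would bar a novel reaction from the top grade. It does not hold, since the second limb already requires a known or expected response pattern.

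**Conclusion.** The point holds as a defect in a stated rule. The first limb of Definitely omits the time sequence that the two lower related grades require and, on the natural reading, the exclusion of other causes. The scale is misordered, and its top grade overlaps with Possibly and, before dosing, with Unrelated.

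The consequence is limited. IRB reporting, the pattern-based stop and the type-defined safety outcomes are largely untouched. The exposed quantity is the numeric SAE stop, and the direction is an undercount. That effect needs two conditions together: the first limb of Table 2, and the omission of definite events from the numeric sentence in Section 14.1. At an assumed 1% rate with half the related SAEs graded Definitely, the chance of reaching four counted SAEs is 21% instead of 68%. This is an illustration and not an estimate. It assumes that Table 2 grades feed the stop and that its wording is applied literally.

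**What to change.** - In the Definitely row, delete the first limb, or join it to the rest with *and*. The grade then requires a reasonable time sequence, a known or expected pattern and no other reasonable explanation.
- State that an event starting before the first dose cannot be graded as related to the drug, and that its relation to the mail-order intervention is judged separately.
- Reconcile the two sentences in the third stopping criterion of Section 14.1, which name different sets of related grades.
- Re-grade any SAE that has been rated Definitely on known toxicity alone.

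Reconciling Section 14.1 by itself would deal with the count but leave the scale misordered, so both changes are needed. The cost is a short protocol amendment with IRB approval, a note to sites, and review of any affected SAE forms. A few events may end up with a lower grade.

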Mail-order pharmacy dispensing of Mifeprex® would not affect the standard of care or recommended clinical protocol for MA in terms of the medication, dosage, timing, and follow-up care. Mifeprex® would also still be prescribed to patients by clinicians who are certified prescribers of Mifeprex® following the current standard assessment of eligibility for medication abortion. The only difference in the provision model to be evaluated in this study is that the patient would obtain the mifepristone directly from a mail-order pharmacy, rather than in a clinic facility.

As noted above, home administration of Mifeprex® is now allowed under the updated Mifeprex® labeling (FDA 2016). Study participants will be told by the prescribing clinician when they should take the Mifeprex®, and participants will be contacted three days later to determine if they received the medications in the mail and if they took the medication as prescribed.

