We are unable to similarly assess whether the prevalence of clinically significant adverse events differs between the mail-order dispensing model and historical controls given the very low frequency of this outcome (<0.5%) (Upadhyay, Desai et al. 2015). A sample size of over 10,000 is required to power such an analysis and is not feasible in the proposed study. Thus, our analysis of safety outcomes will be exploratory. Using a patient survey and medical record review, we will thoroughly document women's experiences with any adverse events. In particular we will be interested in documenting adverse events that could be related to mail-order dispensing. For example, if the delivery of the medication was delayed, which caused a patient to undergo medication abortion after 70 days gestation and she had heavy bleeding requiring an emergency department visit, we would consider this to be possibly related to the mail-order dispensing model. Additional safety outcomes include the proportion of participants who take mifepristone after 70 days gestation and the proportion that divert the medication to someone else.

Provider acceptability, including clinician and staff perspectives on the timing and logistics, quality of care, clinic flow, cost, and sustainability of the mail-order dispensing of mifepristone and misoprostol, will be explored through qualitative analysis of in-depth open-ended interviews. We will invite all clinicians and staff who were involved in identifying and recruiting patients, communicating with the mail-order pharmacy, and/or following up with patients about their clinical care in the study, to participate in an interview at the end of the study period.

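### The only defined causality scale rates relation to the drug and demands a known response pattern, so events new in nature, and SAEs before intake, have no valid related grade

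*Combined protocol and SAP*

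**What the plan says.** Section 12.1.2 states: "The relationship of an AE to the study drug should be assessed using the following the guidelines in Table 2". In Table 2, Possibly, Probably and the second route to Definitely each require a temporal sequence from drug administration and a known or expected response pattern. The wording for Possibly is that the event "follows a reasonable temporal sequence from administration of the drug; that follows a known or expected response pattern to that suspected drug", with other explanations also plausible. The first route to Definitely is a previously known toxicity of the agent. Unrelated is "An event that can be determined with certainty to have no relationship to the study drug".

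The provisions that use the rating name other objects:

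- **Section 12.1** speaks of relation to study treatment, has a form item for relation to the study, and makes submission to the UCSF IRB depend on relation to the research. It also says: "An unexpected AE is one of a type not identified in nature, severity, or frequency in the current Mifeprex® label".
- **Section 14.1** stops the study if more than 0.84% (n=4) of abortions "result in an SAE that is possibly or probably related to the study intervention". A separate rule there looks for a pattern of related events raising concern about the mail-order model.
- **Section 16.4** describes a late delivery, intake after 70 days and heavy bleeding with an emergency visit, and says "we would consider this to be possibly related to the mail-order dispensing model".

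AEs are collected from enrollment (12.1) and SAEs from consent (12.2.1), in both cases before the drug is taken.

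**The concern.** The trial evaluates a dispensing route. Section 2 says "The only difference in the provision model to be evaluated in this study is that the patient would obtain the mifepristone directly from a mail-order" dispenser, not the clinic. The safety rules therefore need a rating that can capture harm from dispensing as well as harm from the drug. They also need one that can flag something not seen before. The defined scale does neither cleanly. It has no graded definitions for relation to mailing, and its lowest related grade excludes anything outside the known drug pattern.

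Two things are at stake. An unexpected event could miss the IRB submission because no related grade fits it. An SAE could also drop out of the 14.1 count, or be handled differently from site to site, across 15 to 20 sites where each site PI makes the rating in consultation with the study PI.

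**Working it through.** **1. Two kinds of event set against Table 2.**

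| Grade | Event new in nature, after intake | SAE between prescribing and intake |
|---|---|---|
| Definitely | Fails: not a known toxicity, no known pattern | Fails: no drug taken, so neither a toxicity nor a sequence from administration |
| Probably | Fails on pattern | Fails on sequence |
| Possibly | Fails on pattern | Fails on sequence |
| Unrelated | Only if certain | Fits, as far as the drug is concerned |

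The first kind may have no grade at all. The second is correctly unrelated to the drug, but nothing says how to grade its relation to the mail-order route. The window is real: section 10.1 tells patients to expect delivery within 3 business days, and 14.1 provides for delays of more than 7 days.

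Only events unexpected *in nature* are caught by the pattern condition. Section 12.1 also calls an event unexpected when its severity or frequency exceeds the label, and such an event can still follow a known pattern.

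**2. The 14.1 threshold.** Inputs from 14.1: background rate p = 0.3%, n = 465, printed limits −0.24% to 0.84%, count 4. Formula: p ± 1.96·√(p(1−p)/n).

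- n = 465: 0.003 ± 0.00497, or −0.20% to 0.80%.
- n = 400: 0.003 ± 0.00536, or −0.24% to 0.84%.

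The printed limits are those for 400, not the stated 465. The count is unaffected: 0.84% × 465 = 3.9 and 0.80% × 465 = 3.7, both rounding up to 4, and 4/465 = 0.86%. I therefore take 4 as reaching the rule. At background alone, 0.003 × 465 = 1.4 SAEs are expected, and the binomial P(X ≥ 4) is 0.053.

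**3. What an ungradable share would do.** The documents give no rate for SAEs before intake or new in nature, so both inputs here are assumptions: a true rate r of SAEs that ought to count, and a share s that Table 2 leaves without a related grade. P(X ≥ 4) with n = 465 and rate r(1−s):

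| r | s = 0 | s = 25% | s = 50% |
|---|---|---|---|
| 1% | 0.68 | 0.46 | 0.21 |
| 2% | 0.98 | 0.92 | 0.68 |

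**4. What the count should include.** Suppose mailing adds an excess e to the 0.3% background. P(X ≥ 4) in 465:

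| e | Background plus excess (0.3% + e) | Mail-attributed only (e) |
|---|---|---|
| 0.3% | 0.31 | 0.05 |
| 0.5% | 0.51 | 0.21 |
| 1.0% | 0.85 | 0.68 |

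A limit of 4 derived from a background rate works only if background events are counted.

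**The case against.** The strongest reply is that nothing ties the 14.1 rules to Table 2. The numeric rule refers to the study intervention, the pattern rule to the mail-order model, and the AE/SAE form already has an item for relation to the study. Section 16.4 shows that the investigators would attribute a delay-caused event to mailing. This stands, and it defeats a reading that a reader might be tempted to adopt: that events caused by the mail wait cannot be rated and cannot reach the stopping rule. The 16.4 example is itself heavy bleeding after intake, a known drug pattern, so Table 2 would not exclude it. What the reply does not supply is a definition of the grades for anything other than the drug.

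Safeguards that need no causality rating also exist:

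- Section 14.1 halts the study temporarily after 3 deliveries delayed by more than 7 days and investigates every delivery after more than 4 days.
- It has triggers at 12 cases of intake after 70 days and 4 cases after 84 days, and the study PI reviews every AE and SAE.
- Section 12.2.1 documents all SAEs whether or not drug-related, and 18.2 sends serious events to the IRB regardless of causality.

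These narrow the gap. The IRB problem is then mainly one of non-serious unexpected events. Section 18.2 also mentions unexpected events, but under the IRB's own policies, and 12.1 describes the UCSF requirement as depending on relatedness. The delivery and gestational-age triggers count delays and late intake, not harm: one SAE during a 5-day delay would prompt an investigation of the delivery but would not add to either count.

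A reader might also infer that counting ordinary drug events in 14.1 is a flaw, making the safety signal wrong in both directions. The documents do not support that. The limit is built on a 0.3% background rate, so counting background events is what the comparison requires.

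**Conclusion.** The point holds as a defect of definition. Under Table 2 as written, an event new in nature has no valid related grade, which conflicts with section 12.1's expectation that unexpected events can be rated related. An SAE before intake has no related grade on the drug scale, and no graded scale exists for the study intervention or the mail-order model named in 14.1 and 16.4. For IRB reporting the effect falls mainly on non-serious unexpected events; through the relatedness filter in 14.1 it also touches SAEs.

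The size cannot be estimated from the documents. The fall from 0.68 to 0.46 rests on an assumed 1% rate, an assumed 25% ungradable share, and sites applying Table 2 literally. A site PI using judgment could avoid the loss, at the price of inconsistency between sites. The point is worth correcting because the correction is cheap, not because missed events have been shown to be numerous.

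**What to change.** 1. In Table 2, remove the known-or-expected-pattern condition from Possibly, so that an event new in nature can be rated related.
2. Reconcile sections 12.1, 12.1.2 with Table 2, 14.1 and 16.4. Specify that the form's existing item on relation to the study is graded twice: for the drug and, separately, for mail-order dispensing. The second grade should be assessable whether or not drug was taken.
3. State in 14.1 that the SAE count includes SAEs at least possibly related to either, which keeps the threshold consistent with its 0.3% basis. This wording also covers Definitely, which the numeric rule does not list although the pattern rule does. The count should not be restricted to mail-attributed SAEs: against the same limit of 4, the chance of stopping at a 0.3% excess would be 0.05 rather than 0.31.
4. Report both ratings in the safety results.

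The cost is short wording changes and one further rating within an existing form item. The downside is that a few more events will be rated possibly related and reported.
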